	5.3.5	Biomarker Analyses including Immune Function and MRD	55	
5.4	Proces	ss for Decision on the Optional Expansion to Phase 3	57	
6.	ASSES	SSMENT OF SAFETY	57	
6.1		nenting and Reporting of Adverse and Serious Adverse Events		
	6.1.1	Adverse Event Reporting Period	58	
	6.1.2	Assessment of Adverse Events	58	
	6.1.3	Pregnancy		
	6.1.4	Expedited Reporting Requirements for Serious Adverse Events		
	6.1.5	Reporting Adverse Events of Special Interest		
	6.1.6	Type and Duration of Follow-up of Subjects after Adverse Events	. 59	
7.	STUDY	Y ADMINISTRATION AND INVESTIGATOR OBLIGATIONS	59	
7.1	Institutional Review Board and Independent Ethics Committee60			
7.2	Informed Consent and Protected Subject Health Information Authorization 60			
7.3	Subject Screening Log60			
7.4	Case Report Forms61			
7.5	Investi	gational Study Drug Accountability	61	
7.6	Record	d Retention	. 61	

8.	REFERENCES	62
APPE	NDICES	65
APPE	NDIX 1. SCHEDULE OF ASSESSMENTS (OBSERVATION AND TREATM ARM)	
APPE	NDIX 2. PERFORMANCE STATUS SCORES	68
APPE	NDIX 3. LIST OF PROHIBITED AND CAUTIONARY MEDICATIONS	69
APPE	NDIX 4. ADVERSE EVENT ASSESSMENT OF CAUSALITY	71
APPE	NDIX 5. CUMULATIVE ILLNESS RATING SCALE (CIRS)	72
APPE	NDIX 6. TUMOR LYSIS PROPHYLAXIS	82
APPE	NDIX 7. CHARLSON COMORBIDITY INDEX	90
APPE	NDIX 8. RESPONSE AND OUTCOME ASSESSMENT	91
APPE	NDIX 9. QUESTIONNAIRES	94
	IN-TEXT FIGURES	
la	1-1. No improvement in infectious deaths despite improvement in overall survival destinated decades	14
	1-2. Competing risk for either infection, CLL treatment or death as first event from iagnosis	
Figure M	1-3. Factors with impact on risk of infection based on regular multiple regression (lachine Learning (right, incomplete list, not completed)	left) and 15
Figure	3-2. Performance of the CLL-TIM predicting high risk CLL patients for infection an eatment at time of diagnosis.	d/or

STUDY SYNOPSIS

Study Title:	Short-term combined acalabrutinib and venetoclax treatment of newly diagnosed patients with CLL at high risk of infection and/or early treatment, who do not fulfil IWCLL treatment criteria. A randomized study with extensive immune phenotyping. PreVent-ACall	
Study Drug:	ACALABRUTINIB (ACP-196) VENETOCLAX (ABT-199)	
Phase:	Phase 2 with option for extension to phase 3 upon analysis of phase 2 part and agreement between study groups and companies	
Comparator:	Observation according to IWCLL criteria	
Study Centers:	Subjects will be enrolled in approximately 7 centers in Denmark, Sweden and the Netherlands.	
Study Objectives:	The aim of the study is to evaluate whether short-term, pre- emptive combination treatment with venetoclax plus acalabrutinib in patients with high risk of infection and/or CLL treatment can change the natural history of immune dysfunction in CLL in terms of the long-term risk of serious infections and diminish the need for cytotoxic chemotherapy. (Without an increased risk of infection during treatment in that group)	
	Primary Objective phase 2 part:	
	 Grade ≥3-Infection-free survival in the treatment arm compared to the observation arm 12 weeks after finishing treatment, (24 weeks after treatment initiation). This is a non-inferiority analysis as detailed in the statistical analysis plan to assure safety of the combination treatment in this preemptive trial population. 	
	Primary Objective optional phase 3 part:	
	 Grade ≥3-infection free and CLL-treatment-free survival 2 years after enrollment 	

Secondary Objective(s):

- Grade ≥3-infection free and CLL-treatment-free survival at end of treatment, 1 year and 2 years after enrollment
- Rate of overall survival (OS) and cause of death
- Treatment free survival
- Rate and CTCAE V5.0 grade of infections
- Response rate and duration according to IWCLL criteria
- Treatment related adverse events, type, frequency and severity during and for 2 years after treatment
- Immune function as assessed by immune phenotyping, functional TruCulture assays and measurements of cytokine levels

Exploratory Objective(s):

- MRD levels in bone marrow and peripheral blood
- Quality of life during and for 2 years after treatment, QLQC30 and CLL17

Study Design:

Newly diagnosed patients with CLL will be assessed by the CLL-TIM algorithm for high risk of infection and/or early CLL treatment need during the screening period. Only patients identified as at high risk, who do not currently fulfil IWCLL treatment criteria, will enter the trial. Assessment of variables for the risk profile including the baseline characteristics and laboratory result based Machine Learning algorithm CLL-TIM will be performed centrally through a plug & play model, which will be part of the eCRF system.

Randomization has to occur within 42 days after the first tests for screening were performed. Patients will be randomly assigned to treatment vs observation through 1:1 randomization process with stratification according to country, TP53 aberration status and IGHV mutational status. Treatment or observation period has to be initiated within 14 days after randomization.

Acalabrutinib 100 mg BID from cycle 1 day 1 for 3 cycles of 28 days. Due to the preemptive treatment within the trial of patients not fulfilling IWCLL criteria for treatment of CLL, the tumor burden will be lower than in other trial populations, thus it is assessed safe to start acalabrutinib and venetoclax treatment simultaneously.

Venetoclax, ramp up during the first five weeks starting cycle 1 day 1, 7 days treatment on each dose level (20-50-100-200-400 mg), thereafter 400 mg once daily for a total of 3 cycles of 28 days counted from cycle 1 day 1.

The trial is a phase 2 trial with a non-inferiority analysis for safety.

Efficacy and Safety Parameters:

Due to the pre-emptive treatment of a patient population normally not treated, an independent Data Safety Monitoring Board (DSMB) will assure ongoing assessment of infectious risk and adverse events. The trial may be stopped based on the decision by the independent DSMB if increased infectious risk or AE risk is considered to outweigh the potential benefit during enrollment. For these safety assessments, the treatment period (first 3 cycles of 28 days each) and the follow up period will be assessed independently to improve detection of treatment-related events vs late treatment-related events and CLL-related events. The following early stopping rules will be applied:

- Any fatal events or Grade ≥3 infectious events in the treatment arm will be reported immediately (within 7 days of notification) to the DSMB for assessment of whether the event impacts the risk-benefit of the treatment (data on similar events in the observation arm will be made available to the DSMB). All Grade ≥3 infectious events would be considered AESIs to be reported along with SAEs within 24 h in the phase 2 part.
- Assuming the incidence of grade ≥3 infectious events is the same in the treatment arm and the observation arm, which based on the predictive model is 10% within the first 6 months, a non-inferiority test can be performed. With a power of 80% and a sample size of 25 patients in each arm, the margin for assessment of non-inferiority will be 21%, i.e. if significantly more infections are seen in the treatment arm than in the observation arm, the treatment arm will be inferior to observation. From a clinical perspective, the margin of error is considered meaningful. The 21% margin of error is acceptable for this high-risk patient population at 24 weeks after initiating treatment/observation, particularly as clinical benefit of treatment is expected to continue for several years.
- Any pattern of AEs or individual AEs through the abovementioned DSMB assessment that indicate that the trial should be stopped.

A thorough translational immune phenotype and immune function analysis plan is adjoined to the study. Results of this translational program are included as secondary outcomes. The assessment of the grade ≥3-infection free, CLL-treatment-free survival will be qualified by the results from the translational program. Hereby, the clinical outcome from the study will be significantly strengthened by molecular and functional information about improvements in immune function.

Immune phenotyping: A 10-color flow cytometry whole blood Biomarker panel comprising 10 different tests has been custom-designed Parameters: (DuraClone, Beckman Coulter) and is currently under validation at the Dept. of Clinical Immunology, Rigshospitalet. The ten different flow tests (I-X) evaluates: I) Major cell lineages in the blood (proportions and counts), II) B cell subsets, III) T cell subsets, IV) T cell receptor (TCR) subsets, V) Regulatory (T_{reg}) and Th₁₇ cells, VI) Dendritic cells, VII) Myeloid cells, VIII) Erythrocytes as surrogates for asplenism, IX) Platelets and platelet-leukocyte co-aggregates and X) Neutrophil phagocyte function. The panel captures multiple patterns predictive for cancer patients i.e. deviated maturation, acute/chronic activation, exhaustion, migration/trafficking and expression of immune checkpoint markers (PD-1, PD-1L, CTLA-4, FoxP3, Helios, CD25, TLR2, TLR4, CD38) which will also be extended with assessment of NK cell function and subtypes as well as additional immune activation markers.1-8 **Immune function**: Stimulated immune response & platelet function are assessed by TruCulture® (Myriad RBM), which assesses the induced innate and adaptive immune responses to whole blood ligand stimulation. Five different stimuli I-V are applied to screen the response to signaling pathways via Toll Like Receptors (TLRs), critical for the anticancer immune response as TLR ligands may break tolerance to self-antigens and promote immune responses to tumor antigens^{9,10}: I) Zymosan; II) Poly I:C; III) Resiguimod; IV) ODN + LPS and V) NegCo. TruCulture® are currently validated at the Dept. of Clinical Immunology, Rigshospitalet and being tested for assessment of immune function in CLL at baseline and during treatment with targeted small molecules. TruCulture® provides an extensive data-readout, with cytokine response data available within days whereas Multiplate®/TEG® provides real-time results also on platelet function and complement cascades. Furthermore, transcriptomics by RNAseg assures in depth analyses of the molecular basis for immune changes upon treatment in stimulated and unstimulated cells. Sample Size: A sample size of 25 patients in each arm, 50 patients in total for the phase 2 part. CLL diagnosed according to IWCLL criteria within one year **Inclusion Criteria:** prior to randomization 2. High risk of infection and/or progressive treatment within 2 years according to CLL-TIM 3. IWCLL treatment indication not fulfilled 4. Life expectancy > 2 years 5. Age at least 18 years 6. Ability and willingness to provide written informed consent and adhere to study procedures and treatment

- 7. Adequate bone marrow function as indicated by platelets above 100 x 10E9, hemoglobin above 10 g/dL and neutrophils above 1 x 10E9
- Creatinine clearance above 30 mL/min directly measured with 24hr urine collection or calculated according to the modified formula of Cockcroft and Gault
- 9. Adequate liver function as indicated by a total bilirubin $\leq 2 x$, AST or ALT $\leq 2.5 x$ the institutional ULN value, unless directly attributable to the patient's CLL or to Gilbert's Syndrome.
- 10. Negative serological testing for hepatitis B (HBsAg negative and anti-HBc negative; patients positive for anti-HBc may be included if PCR for HBV DNA is negative and HBV-DNA PCR is performed every month until 12 months after last treatment cycle), negative testing for hepatitis C RNA within 6 weeks prior to registration.
- 11. Eastern Cooperative Oncology Group Performance Status (ECOG) performance status 0-2.
- 12. Woman of childbearing potential (WOCBP) who are sexually active must use highly effective methods of contraception during treatment and for 30 days after the last dose of investigational drugs.
- 13. Willing and able to participate in all required evaluations and procedures in this study protocol including swallowing capsules without difficulty.
- 14. Ability to understand the purpose and risks of the study and provide signed and dated informed consent and authorization to use protected health information.

Exclusion Criteria:

- 1. Prior CLL treatment (including monoclonal antibodies, chemotherapy, small molecules, including CD20 antibodies, BTK inhibitors and bcl-2 inhibitors for any indication)
- 2. Transformation of CLL (Richter's transformation)
- 3. Previous autoimmune disease as AIHA (autoimmune hemolytic anemia) or ITP (idiopathic thrombocytopenic purpura) treated with immune suppression or uncontrolled AIHA or ITP
- 4. History of progressive multifocal leukoencephalopathy
- 5. HIV infection (a negative test required)
- 6. Known active infection
- 7. Malignancies other than CLL requiring systemic therapies (except anti-hormonal therapies) or considered to impact survival
- Requirement of therapy with strong CYP3A4 and CYP3A5 inhibitors/inducers or anticoagulant therapy with vitamin K antagonists
- 9. History of bleeding disorders or current platelet inhibitors or anticoagulant therapy
- 10. History of clinically significant cardiovascular disease such as arrhythmias, congestive heart failure, or myocardial infarction within 6 months of screening, or any Class 3 or 4 cardiac disease as defined by the New York Heart Association

- Functional Classification, or corrected QT interval (QTc) > 480 msec at screening.
- 11. History of stroke or intracranial hemorrhage within 6 months prior to registration.
- 12. Use of investigational agents which might interfere with the study drug within 28 days prior to registration.
- 13. Vaccination with live vaccines within 28 days prior to registration.
- 14. Major surgery less than 30 days before start of treatment. Note: If a subject had major surgery, they must have recovered adequately from any toxicity and/or complications from the intervention before the first dose of study drug.
- 15. Known hypersensitivity to any active substance or to any of the excipients of one of the drugs used in the trial.
- 16. Pregnant women and nursing mothers (a negative pregnancy test is required for all women of childbearing potential within 7 days before start of treatment; further pregnancy testing will be performed regularly).
- 17. Fertile men or women of childbearing potential unless: surgically sterile or ≥ 2 years after the onset of menopause or willing to use two methods of reliable contraception including one highly effective contraceptive method (Pearl Index <1) and one additional effective (barrier) method during study treatment and for 30 days after the end of study treatment.
- 18. Legal incapacity.
- 19. Persons who are in dependence to the sponsor or an investigator
- 20. Persons not considered fit for the trial by the investigator
- 21. Malabsorption syndrome, disease significantly affecting gastrointestinal function, or resection of the stomach or small bowel that is likely to affect absorption, symptomatic inflammatory bowel disease, partial or complete bowel obstruction, or gastric restrictions and bariatric surgery, such as gastric bypass.
- 22. Prothrombin time/INR or aPTT (in the absence of Lupus anticoagulant) > 2x ULN.
- 23. Requires treatment with proton pump inhibitors (e.g., omeprazole, esomeprazole, lansoprazole, dexlansoprazole, rabeprazole, or pantoprazole). Subjects receiving proton pump inhibitors who switch to H2-receptor antagonists or antacids are eligible for enrollment to this study.

Dose Regimen/Route of Administration:

Acalabrutinib is provided as hard gelatin capsules for oral administration approximately every 12 hours.

Venetoclax is provided as tablets for oral administration once daily

Concomitant Medications:

Prohibited Concomitant Therapy

[figure not shown]
Prohibited (strong CYP3A inhibitors and warfarin/vitamin K antagonists) and cautionary medications are defined as moderate CYP3A inhibitors, and moderate and strong CYP3A inducers.

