5.3.3 Analysis of Primary Endpoint

PRIMARY ENDPOINT, PHASE 2 PART:

Grade ≥3-Infection-free survival in the treatment arm compared to the observation arm 24 weeks after treatment/observation is initiated. The proportion of patients with the primary endpoint will be assessed at 24 weeks after enrollment using a chi-squared test of proportions. - This is a non-

inferiority analysis as detailed in statistical analysis plan to assure safety of the combination treatment in this preemptive trial population.

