6. ASSESSMENT OF SAFETY

Due to the pre-emptive treatment of a patient population normally not treated, an independent DSMB assessment of infectious risk and adverse events on an ongoing basis during enrollment is included. The trial may be stopped based on the decision by the independent DSMB if increased infectious risk or AE risk is considered to outweigh the potential benefit. For these safety assessments, the treatment period (first 6 cycles of 28 days each) and the follow up period will be assessed independently to improve detection of treatment-related events vs CLL-related events. The following early stopping rules will be applied:

- Any fatal events or Grade ≥3 infectious events in the treatment arm will be reported immediately (within 7 days of notification) to the DSMB for assessment of whether the event impacts the risk-benefit of the treatment (data on similar events in the observation arm will be made available to the DSMB). All Grade ≥3 infectious events would be considered AESIs to be reported along with SAEs within 24 h in the phase 2 part.
- Assuming the incidence of grade ≥3 infectious events is the same in the treatment arm and
 the observation arm, which based on the predictive model is 10% within the first 6 months, a
 non-inferiority test can be performed. With a power of 80% and a sample size of 25 patients
 in each arm, the margin for assessment of non-inferiority will be 21%, i.e. if significantly more

infections are seen in the treatment arm than in the observation arm, the treatment arm will be inferior to observation.

- Any pattern of AEs or individual AEs through the above-mentioned DSMB assessment that indicate that the trial should be stopped.
- A thorough translational immune phenotype and immune function analysis plan is adjoined to the study. Results of this translational program are included as secondary outcomes. The assessment of the grade ≥3-infection free, CLL-treatment-free survival will be qualified by the results from the translational program. Hereby, the clinical outcome from the study will be significantly strengthened by molecular and functional information about improvements in immune function.

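### The stated 80% power for the 21-point non-inferiority margin rests on a normal approximation; with 25 per arm, a score test that keeps close to its one-sided 5% level has about 72%.

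*Protocol*

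**What the plan says.** The calculation stands in the Study Synopsis (Efficacy and Safety Parameters) and is repeated in Section 6.

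- Event rate: "Assuming the incidence of grade ≥3 infectious events is the same in the treatment arm and the observation arm", a rate that "based on the predictive model is 10% within the first 6 months".
- Power, size and margin: "With a power of 80% and a sample size of 25 patients in each arm, the margin for assessment of non-inferiority will be 21" percent. Section 6 has the same words: "in each arm, the margin for assessment of non-inferiority will be 21" percent.
- Allocation and total: "Patients will be randomly assigned to treatment vs observation through 1:1 randomization process"; "A sample size of 25 patients in each arm, 50 patients in total for the phase 2 part".
- Test, in Section 5.3.3: "The proportion of patients with the primary endpoint will be assessed at 24 weeks after enrollment using a chi-squared test of proportions". The same section describes this as a non-"inferiority analysis as detailed in statistical analysis plan to assure safety of the combination treatment in this preemptive trial population".

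The protocol gives no significance level, sidedness or variance method with the power figure. Section 5.4 lists meeting the phase 2 non-inferiority criterion among five inputs to the decision on the optional phase 3 expansion.

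**The concern.** At a 10% rate, 25 patients give 25 × 0.10 = 2.5 expected events per arm. A normal approximation to a difference of two such proportions is poor, and a power figure taken from it may not belong to any test that keeps its nominal error rate. If the stated 80% is optimistic, the sponsor is accepting a larger chance than it intends that a regimen with no excess infection fails the phase 2 criterion. That criterion also feeds the phase 3 decision. The opposite error matters too. A test that does reach 80% by running above its level passes a regimen at the margin more often than the nominal 5%, in patients who would normally not be treated.

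**Working it through.** **Inputs.** Rate 10% in both arms (true difference 0), n = 25 per arm, margin 21 percentage points, power 80%: synopsis and Section 6. Allocation 1:1: synopsis. Level: not given with the calculation, so inferred below. All 25 per arm are taken as evaluable at 24 weeks.

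**Reproducing the stated figure.**

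SE = √(2 × 0.10 × 0.90 / 25) = √0.0072 = 0.0849.

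- Margin for 80% power at one-sided 5%: (1.645 + 0.842) × 0.0849 = 0.211.
- Power at a margin of 0.21: Φ(0.21/0.0849 − 1.645) = Φ(0.830) = 79.7%.

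The protocol's 21% and 80% are therefore the unpooled normal approximation at one-sided 5%. Other variants do not return them. One-sided 10% gives a margin of 18.0 points, and one-sided 2.5% gives 23.8. An ordinary chi-squared comparison of 10% with 31% has 58% power one-sided and 45% two-sided.

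**Exact check.** All 26 × 26 outcomes were enumerated with binomial probabilities at n = 25, at one-sided 5%. Power is taken at 10% versus 10%, and size at 31% (treatment) versus 10% (control). The maximum size is taken over all control rates.

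| Test against the 21-point margin | Power | Size at 31% vs 10% | Maximum size |
|---|---|---|---|
| Unpooled Wald | 81.9% | 6.2% | 8.9% |
| Agresti-Caffo | 77.3% | 5.9% | 8.0% |
| Newcombe | 75.4% | 5.8% | 6.1% |
| Score (Farrington-Manning) | 72.3% | 4.7% | 5.4% |
| Exact unconditional, score ordering | 72.3% | 4.6% | 4.9% |

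The other statistics, with cut-offs tightened until the maximum size is at most 5%, have 58% to 66%. No test examined has both 80% power and a held 5% level.

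**Where the difference arises.** At 10% in both arms, only three outcomes of any weight pass under Wald and fail under the score test. In order (treatment events, control events) they are (2, 0), (3, 1) and (4, 3). The binomial probabilities for 0, 1, 2, 3 and 4 events are 0.0718, 0.1994, 0.2659, 0.2265 and 0.1384, so:

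- (2, 0): 0.2659 × 0.0718 = 0.019
- (3, 1): 0.2265 × 0.1994 = 0.045
- (4, 3): 0.1384 × 0.2265 = 0.031

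The sum is about 0.096, the whole gap between 81.9% and 72.3%.

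Take (3, 1). The observed difference is 0.12 − 0.04 = 0.08. The Wald standard error is √[(0.12 × 0.88 + 0.04 × 0.96)/25] = 0.0759, so z = (0.08 − 0.21)/0.0759 = −1.71 and the outcome passes. The score test uses the variance fitted at the margin (rates of about 0.235 and 0.025): √[(0.235 × 0.765 + 0.025 × 0.975)/25] = 0.090. This gives z of about −1.44, and the outcome fails. With few events, Wald understates the variance at the boundary being tested.

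**Sensitivity to the control rate.** Score test, equal rates in both arms, one-sided 5%: 76.9% power at 8%, 72.3% at 10%, 68.0% at 12%.

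**The case against.** The strongest reply is that no figure is wrong. The inputs return the stated margin by a standard planning formula, and the test statistic, level and sidedness are matters that the protocol refers to a statistical analysis plan not seen here. That stands. A reader might infer an arithmetic error, or a fault in the absence of alpha from the protocol, and neither inference is supported. What remains is that the protocol itself publishes the power, twice, and the figure is optimistic for a test that holds its level.

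A second reply is that 72% belongs to a test the protocol does not name. This stands in part. An ordinary chi-squared test addresses equality, not a margin; the score test is its margin form, which makes it the natural reading of Section 5.3.3, but the analysis plan may choose otherwise. The uncorrected score test also goes slightly over its level (5.4% at a control rate near 18%). Its exact version does not, and has the same power.

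Several stronger readings are tempting and should not be drawn:

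- **Power of 59% or 70%, from one-sided 2.5%.** Nothing in the protocol points to that level, and the stated margin does not reproduce under it.
- **Further loss of power from dropout.** With 23 or 20 evaluable per arm the score test would have about 68% or 63%, but those numbers are pure assumptions. Sections 3.13 and 4.3 keep patients in follow-up after treatment stops, and the horizon is only 24 weeks.
- **A missed test ends the programme.** Section 5.4 lists non-inferiority as a condition that should be met, but among five inputs, and the sponsor decides.
- **The margin is too wide because it allows 10% to rise to 31%.** That concerns the choice of margin, for which the synopsis gives its reasoning, and not the power.

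**Conclusion.** The concern holds as a point about optimistic power. At the protocol's own inputs and the one-sided 5% level that its figure implies, power is about 72% for a score or exact score test against the margin, not 80%. The chance that a neutral regimen misses non-inferiority is about 28% (1 − 0.723), against the planned 20%. For control rates of 12% to 8% the power is about 68% to 77%.

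This rests on three assumptions: the level is one-sided 5%, the analysis uses a margin test that keeps to its level or very close to it, and all 25 patients per arm are evaluable at 24 weeks. If the analysis plan specifies an unpooled Wald bound, power is about 82%, but the error rate at the margin is then 6.2% and can reach about 9%. The design can stand; the stated power should be corrected.

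**What to change.** Keep 50 patients and the 21-point margin. In the synopsis and in Section 6:

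- State the level that the calculation used, one-sided 5%, once confirmed against the statistical analysis plan.
- Restate power along these lines: with 25 evaluable patients per arm, a 10% risk in both arms and a margin of 21 percentage points, a score or exact score test at one-sided 5% has about 72% power (about 68% to 77% for control rates of 12% to 8%).
- Describe a positive result as excluding an excess of 21 percentage points or more, instead of as assuring safety. Align the wording in Section 5.3.3.

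Leave out figures for one-sided 2.5% or for fewer evaluable patients, or label them as assumptions.

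The cost is a few sentences and a less favourable stated power. No patient, visit or design feature changes.

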5.3 ENDPOINT DATA ANALYSIS

5.3.1 Safety Endpoint(s) for the Phase 2 Part as Primary Endpoint

- Grade ≥3-Infection-free survival 24 weeks after treatment initiation. This is a non-inferiority analysis as detailed in statistical analysis plan to assure safety of the combination treatment in this preemptive trial population.
- Rate and CTCAE grade of infections
- Treatment related adverse events, type, frequency and severity during and for 2 years after treatment

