In addition, an NGS capture-based assay for MRD detection based on recurrent mutations and IGHV sequence is under development. DNA is prepared from patient samples at time of MRD assessment by flow cytometry. After full enrollment, these DNA samples will be analyzed by the NGS assay to allow for direct comparison of MRD assessment by the two methods and to allow for assessment of subclonal development during and after treatment. Furthermore, BH3 profiling as

developed in collaboration with Assoc. [name], Dana Farber Cancer Institute, will be employed for assessment of sensitivity to various targeted therapies of viably frozen primary CLL cells from enrolled patients at baseline. The results of BH3 profiling will be correlated with long term outcome for the patients.

5.4 PROCESS FOR DECISION ON THE OPTIONAL EXPANSION TO PHASE 3

When the phase 2 part of the study is fully enrolled, the following assessments will form the basis for the decision on whether to expand the study to the optional phase 3 part with 212 patients in total:

- Non-inferiority for the phase 2 part as stated above should be met
- Immunophenotype analyses as outlined above have been reviewed
- Trend for benefit for patients in the treatment arm should be assessed
- DSMB do not find contraindications or safety reasons against expansion to phase 3
- Assessment by Abbvie, Acerta and the two study groups have been reviewed

The final decision to expand the study to the phase 3 part will be made by the sponsor, taking into account the input from the above-mentioned analyses and assessments.

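### The protocol glosses its 21% non-inferiority margin as an ordinary test for more infections and names a chi-squared test of equality, so no rule written in it compares the result with 21 points

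*Protocol*

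**What the plan says.** The Synopsis (Efficacy and Safety Parameters) and Section 6 assume the same infection risk in both arms, "which based on the predictive model is 10% within the first 6 months, a non-inferiority test can be performed". They continue: "With a power of 80% and a sample size of 25 patients in each arm, the margin for assessment of non-inferiority will be 21" percent. Both places then restate the margin in words: "if significantly more infections are seen in the treatment arm than in the observation arm, the treatment arm will be inferior to observation".

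Section 5.3.3, on the primary endpoint, names one method: "The proportion of patients with the primary endpoint will be assessed at 24 weeks after enrollment using a chi-squared test of proportions". It adds, as do the Synopsis objectives and Sections 2.1 and 5.3.1, that the non-inferiority analysis is set out in the statistical analysis plan; in 5.3.1 the words are "This is a non-inferiority analysis as detailed in statistical analysis plan to assure safety of the combination treatment".

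Section 5.4 puts the result first among the inputs to the phase 3 decision: "Non-inferiority for the phase 2 part as stated above should be met". The protocol states no alpha and no sidedness.

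**The concern.** A non-inferiority test has to reject the hypothesis that the excess risk is 21 points or more. The written rule asks instead whether equality is rejected in the direction of harm. The two questions reward opposite things. With few patients a margin test is hard to pass, while a test of equality is easy not to fail. About 2.5 events are expected per arm (25 × 0.10), so a non-significant result says little.

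This is the primary safety question of a trial that treats patients who would normally be observed, and a listed condition for expanding to phase 3. The protocol needs a criterion for having met non-inferiority, and the only rule it spells out leaves the margin unused.

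**Working it through.** **Inputs.** From the Synopsis and Section 6: 10% risk in each arm, 80% power, 25 per arm, margin 21 points. Allocation is 1:1 (Synopsis, Section 3.6.4). Alpha is not stated, so a range is shown.

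**The plan's own figure.** Margin = (z₁₋α + z₀.₈₀) × √(2 × 0.10 × 0.90 / 25), where the square root is 0.0849.
- One-sided α = 0.05: (1.645 + 0.842) × 0.0849 = 21.1 points; power at a 21-point margin is 79.7%.
- One-sided α = 0.025: (1.960 + 0.842) × 0.0849 = 23.8 points; power is 69.7%.

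The 21% therefore comes from a genuine non-inferiority formula at one-sided 5%. The sizing uses the margin; the written rule does not.

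**How often each rule passes.** With x events on treatment and y on observation, P(pass) is the sum of Bin(x; 25, p_T) × Bin(y; 25, p_C) over all 26 × 26 outcomes that pass. The written rule passes unless x > y and the test is significant. The margin rules, at one-sided 5%, pass if the Farrington-Manning score test rejects a 21-point excess, or if the Wald upper bound is below 21 points.

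| True risk, treatment vs observation | Written rule, Pearson one-sided 5% | Written rule, Pearson two-sided 5% | Written rule, Fisher two-sided 5% | Score margin test | Wald margin bound |
|---|---|---|---|---|---|
| 10% vs 10% | 94.4% | 97.6% | 99.6% | 72.3% | 81.9% |
| 31% vs 10% (at the margin) | 39.8% | 51.9% | 66.8% | 4.7% | 6.2% |
| 40% vs 10% (beyond it) | 17.9% | 26.6% | 40.9% | 0.8% | 1.0% |

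**A concrete result.** Take 2/25 infections on observation.
- 7/25 on treatment is a 20-point excess. Pearson χ² = 50 × (7×23 − 2×18)² / (25×25×9×41) = 3.39, two-sided p = 0.066, so not a significant excess. The Wald upper one-sided 95% bound is 0.20 + 1.645 × √(0.28×0.72/25 + 0.08×0.92/25) = 37 points, far above 21.
- 8/25 is the first count that is significant (p = 0.034).
- 4/25 (p = 0.38) has an upper bound of 0.08 + 1.645 × √(0.16×0.84/25 + 0.08×0.92/25) = 23 points and already fails the margin.

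So 4 to 7 infections out of 25 on treatment get opposite verdicts under the two rules (two-sided Pearson).

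**The case against.** The strongest reply is that the analysis plan may be right. The protocol defers to it in four places, and in Section 5.3.3 the deferral directly follows the chi-squared sentence. Test statistic, confidence limit and alpha commonly sit in that plan. This stands against one tempting inference, that the margin is never tested: the protocol alone cannot show that. It does not cure the wording, because the protocol does more than stay silent. It states a rule in two places and names a test, and neither uses the margin.

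Second, the protocol says only that a significant excess means inferior. A reader might infer that a non-significant result counts as proof of safety, but no sentence says so. The converse is implied by offering the clause as the meaning of the margin, and by Section 5.4 needing a verdict for which no other criterion is given. One could also read the clause as a significant excess over the margin. The text does not say that, and a chi-squared test of proportions would not deliver it.

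Third, the clause stands among the early stopping rules. The data safety monitoring board reviews each grade 3 or higher infection in the treatment arm, and non-inferiority is one of five inputs to a decision that the sponsor takes. All true: the verdict is not the only safeguard. It is still the primary analysis.

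Fourth, a reader might conclude that a clearly harmful regimen would usually pass. The figures do not support this. At one-sided 5% a regimen at the margin passes 40% of the time, a minority, and at 40% vs 10% the Pearson rule passes 18% or 27%.

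**Conclusion.** The concern holds for the protocol's wording. The margin is sized by a non-inferiority formula, then explained by a rule, and paired with a test, that ignore it. If that rule is used as the pass/fail criterion, a regimen exactly at the margin passes 40% to 67% of the time depending on the test, against about 5% for a margin test. At 40% vs 10% it passes 18% or 27% (Pearson, one- or two-sided), against about 1%.

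This rests on three assumptions: the implied converse is the criterion that Section 5.4 relies on; observation risk is the protocol's 10%; and alpha is 5%, which the protocol does not state. The 21% is not an arithmetic error, since it reproduces at one-sided 5%. What the analysis plan does with the margin is unknown. The wording should be corrected before the primary analysis, because the two documents would otherwise conflict or share the error.

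**What to change.** - In the Synopsis and Section 6, delete the clause that explains the margin by a significant excess of infections.
- In Section 5.3.3, replace the chi-squared test with: non-inferiority is concluded only if the upper one-sided confidence bound (Farrington-Manning or Miettinen-Nurminen score) for the 24-week difference in risk, treatment minus observation, is below 21 percentage points; otherwise non-inferiority is not shown.
- State alpha. One-sided 5% matches the 21% margin, and the choice should be explicit.
- Restate power for the chosen method. With the score bound at one-sided 5%, exact power at 10% vs 10% and 25 per arm is about 72%, not 80%. A Wald bound gives about 82%, but its error rate at the margin is 6.2%.
- Check that the analysis plan uses the same rule.

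The change needs no new data, only an amendment of three places. The real cost is the power statement: with the score bound, the protocol must either accept about 72% or revisit the sample size.
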